9.1.8 EFFICACY & EXPLANT VISIT (IN-PERSON, day 28)

This visit has two parts. The total duration of this visit is expected to be approximately 1 hour.

The first part of the visit is focused on capturing stimulation thresholds of cutaneous afferent nerves to provide information about the Injectrode's capabilities to conduct current at low electrical impedance values. This first part is anticipated to last for approximately 30 minutes and scheduled to occur just before the explant of the Basmati Injectrode insert.

The second part of the visit is the actual explant of the device that will then be sent to histopathology for further processing. This second part is anticipated to last for approximately 30 minutes and will include image capturing for purposes of documentation.

Part I: Impedance and stimulation threshold data acquisition

Materials:

Stimulation will be provided using a DS7A Constant Current Stimulator unit (Digitimer), a device with CE and FDA clearance. Electrical impedance will be measured with a handheld, battery-powered oscilloscope (Fluke ScopeMeter) that is certified and calibrated. Sterile clinical grade standard needles intended for single patient use (30 gauge) will be used to directly interface percutaneously with the Injectrode. Details for this interfacing approach are provided below. A clinical grade, disposable, surface patch electrode will be used as a distal return, referred to as a TENS electrode/patch in this document. The Stimulator, Oscilloscope, Needles and TENS electrodes will be connected together using standard leads (Pamona, Comed).

Methods:

The setup for these stimulation and impedance tests are done under two types of visualization. First, visualization is done via ultrasound according to a Mohs' surgery plan. Second, the setup is visualized with fluoroscopy to ensure that the needles are placed precisely within the subcutaneously implanted Basmati Injectrode.

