All equipment will be turned on prior to use, followed by connecting the Stimulator in parallel to the Oscilloscope as shown in Figures 7a through 7e below. Data will be recorded for every measurement. Prior to beginning the measurements, test leads will also be hooked up to the stimulator in parallel. Generally, measurements during this visit will be recorded at a current amplitude ranging between 0.1 and 10 mA and pulse widths ranging from 50 μ sec to 1500 μ sec. Reference impedance values will be recorded at a current amplitude at 1mA and a pulse width of 200 μ sec using a reference resistor of 1 kOhm. The sensory stimulation thresholds ("Measurement 1" through "Measurement 3.3") below will be conducted with a preferred pulse width of 100 μ sec and 200 μ sec, and, if need be, may be measured once more with a different pulse width in the range between 50 μ sec to 1500 μ sec to be able to capture stable measurements.

In order to record sensory afferent nerve responses to electrical stimulation, it is imperative that lidocaine is not injected at the site of the Injectrode for the entity of part 1. Instead, the skin above the

Injectrode is cleaned using 70% Isopropyl alcohol at the site of the Injectrode with a margin of 3cm around the site, identified via palpation of the skin. Two 30 gauge needles are inserted through the cleaned skin into the Injectrode as shown in Figures 8a through 8e. At a location 1-2cm away from the Injectrode, a third 30 gauge needle will be inserted as shown in Figure 8a. Finally, at a location approximately 10 cm away from the Injectrode, a TENS patch electrode will be placed to function as the return electrode for electrical current. Test leads with hooked ends will be attached to the needle shaft extending out of the skin and taped to the skin to keep the leads secure and from pulling on the needles should the study participant or lead move.

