Measurement 1: Once the leads are properly attached to the needles and TENS patch, testing may commence. The first measurement will establish the stimulation activation (sensation) threshold of afferent nerves in the skin of the hip region of the study participant in the vicinity of where the Injectrode is present. Needle D and TENS patch C will first be connected to the stimulator (as shown in figure 8a), and step wise increments in stimulus amplitude will be performed until the study participant notes that they can perceive the stimulation (e.g. step size amplitude = 100 μ A, pulse width = 200 μ sec). The study participant will be asked to report when they perceive a paresthesia, essentially a tingling sensation of the skin. The current and pulse width values for the initial report of paresthesia will be recorded and may be verified with a second measurement. The values allowing the study participant to perceive a tingling paresthesia sensation are expected to be an order of magnitude smaller than currents needed to cause the perception of pain. If the study participant reports pain during the stimulation then the clinician will adjust their testing approach accordingly to avoid such participant feedback. Once the stimulation activation threshold is determined, lead D may be unplugged and needle D removed from the skin.

[figure not shown]

Figure 8a: Stimulus activation setup of electrodes for measurement #1.

A series of three stimulation tests will be performed between the Injectrode (A, B) and the TENS patch (C), as shown in Figures 8c, 8d, and 8e. The first stimulation for each measurement will be performed at or below the stimulation threshold established in measurement 1 for the study participant. The study participant will be asked whether they sensed the stimulus, and their answer recorded. If needed, the stimulation current will be increased in increments of 100 μ A of current or 50-100 μ sec of pulse duration until the study participant perceives the stimulus.

In **measurement 2** (Figure 8b), needle A and the TENS surface patch electrode (C) will be hooked up to the stimulator and oscilloscope.

[figure not shown]

Figure 8b: Impedance and Stimulation setup of electrodes for measurement #2.

In **measurement 3** (Figure 8c), needle B and the TENS surface patch electrode (C) will be hooked up to the stimulator and oscilloscope.

[figure not shown]

Figure 8c: Stimulation setup of electrodes for measurement #3.

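### Protocol 9.1.8: Measurements 2–4 may start at the Measurement 1 threshold with no step-down and may step pulse duration, so the threshold may be recorded only as a bound before explant

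*Protocol*

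**What the plan says.** All of this is in Protocol 9.1.8, Part I, unless another section is named.

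- **Purpose.** The section opens with "The first part of the visit is focused on capturing stimulation thresholds of cutaneous afferent nerves". Section 2.2 names stimulation thresholds, with impedance, as the secondary outcome.
- **Measurement 1** (separate needle D to patch C) gives the reference threshold, called M1 here. It is searched in amplitude only: "step wise increments in stimulus amplitude will be performed until the study participant notes that they can perceive the stimulation". The example given is 100 µA steps at 200 µs.
- **Three tests between the Injectrode and the patch** follow. On the starting level: "The first stimulation for each measurement will be performed at or below the stimulation threshold established in measurement 1 for the study participant". Then: "The study participant will be asked whether they sensed the stimulus, and their answer recorded". If needed, the stimulus is raised by 100 µA of current or by 50–100 µs of width; that sentence ends "sec of pulse duration until the study participant perceives the stimulus". No step down is written.
- **Pulse width** is covered earlier, in the Methods text: "The sensory stimulation thresholds ('Measurement 1' through 'Measurement 3.3') below will be conducted with a preferred pulse width of 100" µs and 200 µs. A threshold, "if need be, may be measured once more with a different pulse width in the range between 50" and 1500 µs.
- **Labels.** The three tests are described as "between the Injectrode (A, B) and the TENS patch (C), as shown in Figures 8c, 8d, and 8e". Figure 8e, however, is needle A to needle B (Measurement 5). By electrode description the three tests are Measurements 2–4, Figures 8b–8d.

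Amplitudes and widths go into the CRF. The Injectrode is removed in Part II of the same visit.

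**The concern.** A threshold search has to bracket the threshold: one level not felt, and the next level felt. The written rule does not guarantee this for Measurements 2–4, for two reasons.

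1. A test may start exactly at M1 and only goes up. If the first stimulus is felt, the test is over and no level below M1 has been tried.
2. The operator may widen the pulse instead of raising the current. Measurement 1 steps amplitude only, and the Methods text prefers two fixed widths. Nothing says which rule governs, so the current threshold at the M1 width may never be found.

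Both outcomes comply with the protocol. There is one session per participant and at most 10 participants, and the device is then explanted. No later analysis can supply a level that was not tested. Section 1.4 says these recruitment data are meant to support a follow-up study.

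**Working it through.** The protocol gives no expected M1 and no expected ratio for Measurements 2–4, so there is no stated figure to reproduce. The check applies the written rule to assumed values.

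**Inputs from 9.1.8:** current step 0.1 mA; width step 50–100 µs; current range 0.1–10 mA; preferred widths 100 and 200 µs. **Assumed:** M1 of 1, 2 or 4 mA, and a participant who feels a stimulus whenever it reaches a fixed true threshold.

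**Step 1: starting level.** With increases only, recorded threshold = max(true threshold, starting level), rounded up to the next 0.1 mA step. Starting at M1, recorded ratio to M1 = max(true ratio, 1).

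| True ratio to M1 | Recorded, start at M1 (M1 = 1, 2, 4 mA) | Recorded, ascending from 0.1 mA (M1 = 1 mA) | Same (M1 = 2 or 4 mA) |
|---|---|---|---|
| 0.25 | 1.0 | 0.3 | 0.25 |
| 0.5 | 1.0 | 0.5 | 0.5 |
| 0.75 | 1.0 | 0.8 | 0.75 |
| 1.0 | 1.0 | 1.0 | 1.0 |
| 1.5 | 1.5 | 1.5 | 1.5 |

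A test started at M1 cannot record a ratio below 1. Thresholds above M1 are found correctly if current is stepped. At M1 = 1 mA, a 30% lower threshold lies (1 − 0.7)/0.1 = 3 steps down, and none of them is tried. A search that begins low enough recovers the ratio to within one step.

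**Step 2: search variable.** Suppose the first stimulus, at M1 and 200 µs, is not felt and the width is stepped. One, two or three steps end at 250–300, 300–400 or 350–500 µs. The current threshold at 200 µs is then known only to be above M1.

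To gauge what one width step hides, assume a Weiss strength–duration curve, I = Irh(1 + c/PW), with c = 100, 200 or 400 µs:

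- 200 to 250 µs: 1.5/1.4 = 1.07; 2/1.8 = 1.11; 3/2.6 = 1.15.
- 200 to 300 µs: 1.5/1.333 = 1.13; 2/1.667 = 1.20; 3/2.333 = 1.29.

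One width step from 200 µs thus stands in for a 1.07- to 1.29-fold change in current. At M1 = 1 mA that is 0.7 to 2.9 current steps of 0.1 mA; at 2 mA it is 1.4 to 5.7.

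**Step 3: recovery from the record.** The CRF holds amplitude and width, so a reader can see that a value was felt at the first stimulus or reached at another width. That identifies the bound; it does not supply the threshold.

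**The case against.** The strongest reply is that the text is permissive rather than wrong. It already allows a start below M1, and an operator who uses that freedom and keeps to 100 and 200 µs gets a usable current threshold. The protocol also states no expected ratio or success rule for Measurements 2–4; its only stated ratio is Measurement 5 against Measurement 1, where a higher threshold is expected and starting at M1 loses little. Impedance is untouched. The study is an unpowered pilot (11.2), and the outcome is descriptive.

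All of that stands, and it limits the weight of the point. It does not remove it. The section says it is capturing thresholds, uses M1 as the reference level, and allows a compliant search that returns only a bound.

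Two stronger readings are tempting and are not supported.

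- A reader might infer that stepping duration breaks the allowance of one repeat at another width. The repeat is a second threshold measurement, whereas duration steps occur within one search, and the general range runs from 50 to 1500 µs. The defect is only that the two paragraphs do not say which rule governs.
- A reader might infer that the 10 mA limit in Measurement 5 defeats the expected five-fold ratio once M1 exceeds 10/5 = 2 mA. That holds only at one fixed width, other widths are allowed, and the ratio is an expectation rather than a criterion.

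**Conclusion.** The point holds as an optional improvement to a data-acquisition rule. As written, Measurements 2–4 can return an upper bound (felt at M1) or, if duration is stepped, only a lower bound on the current threshold at the M1 width. In the first case every true ratio from 0.25 to 1.0 records as 1; this follows from the rule and does not depend on the M1 assumed. The size of the second effect, 1.07- to 1.29-fold per width step from 200 µs, rests on the assumed curve. How often operators would start at M1 or step duration is unknown.

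Only the threshold half of the secondary outcome is affected. The documents do not support reading this as a flaw in the safety assessment or in impedance, or as a loss of thresholds in every participant. The figure and measurement labels are clerical slips. They matter only because they blur which rule applies to which test.

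**What to change.** For the thresholds in Measurements 2–4:

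- Make the start below M1, which the text already permits, the rule. If the first stimulus is felt, step down until it is not felt, then ascend.
- Step current at the same pulse width as M1. Report any repeat at another width separately, as the Methods text allows.
- In the CRF, code any value felt at the first stimulus with no lower level tested as an upper bound. Code a Measurement 5 value not felt at the existing limit as >10 mA.
- Leave the clinician's discretion on pain and the existing current and width ranges unchanged.
- Reconcile the Methods text with the three-test paragraph on which search rule and figures apply to which measurement. Correct Measurement 3.3, which does not exist, and Figures 7a–7e, evidently 8a–8e.

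**Cost.** The change needs edits to two paragraphs, the figure citations and CRF codes, with no new needles or equipment. The extra stimuli below M1, over three measurements, are:

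- Start one step below M1: 3 × 1 = 3 per width.
- Start at half of M1: 3 × (0.5 × M1/0.1) = 15 per width at 1 mA and 30 at 2 mA. Both widths together need 30 and 60, or 15 × 2.667 = 40 and 30 × 2.667 = 80 if M1 at 100 µs is 1.667-fold higher (the Weiss ratio 5/3 at c = 400 µs).
- Step-downs add a few more. At M1 = 1 mA and a true threshold of 0.7 mA, the levels are 0.9, 0.8, 0.7, 0.6, 0.7: five stimuli instead of one.

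At an assumed 3–5 s each, 3 to 80 stimuli take 3 × 3 = 9 s to 80 × 5 = 400 s, before step-downs. Replacing one duration step from 200 µs also adds current steps above M1, about 1–3 in its place at 1 mA and 2–6 at 2 mA. The total must fit the roughly 30-minute slot in 9.1.8 and the roughly 20-minute exposure in 1.4. The upper figure is a third of that exposure (400/1200), which favours starting only a step or so below M1.

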In the proposed safety study, the Basmati insert will be used as a passive device not intended for diagnosing, curing, mitigating, or treating disease, or otherwise preventing impairment of human health. Prior to removing the device in a minimally invasive procedure, the Injectrode will be briefly interfaced with electrical current using standard electro-acupuncture techniques, following the labeling for these approved devices. The total time of exposure to this limited stimulation period will be approximately 20 minutes right prior to device extraction via Mohs procedure.

- 4. Otherwise presents a potential for serious risk to the health, safety, or welfare of a subject.**

Based on the Neuronoff, Inc. Quality Management System, risks associated with the device will be evaluated and addressed per the Design Control Procedure, SOP-02 and the Risk

Management Procedure, SOP-05 and according with the ISO-14971 Risk Management Standard to assure that the Basmati Injectrode insert is deemed to not represent any potential for serious risk to the health, safety, or welfare of a subject. The minimally invasive placement at a location in the subcutaneous tissue and rigorous follow-up schedule are designed to allow the physician to monitor the response of each study participant very closely and, if necessary, explant the device prior to the 28 day mark without unnecessary risk to the health, safety, or welfare of a subject. The material of the Injectrode is 99.99% gold, a material commonly used in neuromodulation electrodes that is biointert and very well received by humans clinically. The method of removing the Injectrode at the end of the safety study will follow a procedure similar to a Mohs procedure, a standard clinical practice that poses little risk to study subjects. Subjects will be followed for signs of inflammation of the surgical site, granulomas, irritation.

This early feasibility study aims to document the clinical biological response to an Injectrode, roughly the size of a Basmati rice grain, placed temporarily into up to 10 healthy volunteers for a duration of up to 28 days. The efficacy of the device is assessed by measuring electrical and sensory nerve recruitment data immediately prior to explanting the device. These data are intended to provide rationale for a follow-up study testing a therapeutic intervention.

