5.0 OUTCOMES

The outcomes of the study are focused on collecting data to determine clinical outcomes of placing the Basmati Injectrode for up to 28 days in healthy study participants to 1) assess tissue responses and, on the last day just prior to explant, 2) collect data describing the quality of the electrical interfacing with the Injectrode from outside of the body, as well as with subcutaneous sensory nerves surrounding the Injectrode insert.

Safety data will also be collected at all visits. Data will be collected using:

- True color images of the surgical site and the insert placement location.
- Ultrasound and fluoroscopy (x-ray) images of the insert placement location.
- CRFs to capture any pain or discomfort, AEs and UPs.
- Patho-histological data from tissue samples collected during the explant procedure (Injectrode with approximately 0.5 to 1mm of naïve tissue in Mohs style procedure).

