In **measurement 4** (Figure 8d), needles A and B will be connected together to one output/input, while the TENS surface patch electrode (C) will be hooked up to the other output/input of the stimulator and oscilloscope.

[figure not shown]

Figure 8d: Stimulation setup of electrodes for measurement #4.

Measurement 5: Lastly, needles A and B will be hooked up to the stimulator as shown in Figure 8e. Electrical stimulation at the stimulus activation threshold will be applied. The study participant will be asked if they still perceive the stimulation at threshold. If they do not, another stimulus activation threshold test will be performed (e.g. step size amplitude = 100 μ A, pulse width = 200 μ sec) up to 10 mA of current. After each stimulation, the study participant will be asked if they perceived the stimulation, with perception noted as the stimulus activation threshold of current passing through the injectrode. It is expected that the threshold in Measurement 5 will be at least five times higher than that recorded in Measurement 1, as a result of the conductive injectrode shunting (short-circuiting) current between the two needles, thus making it harder to stimulate nerves near the Injectrode. Recorded data from the oscilloscope will be used to calculate the impedance of the Basmati Injectrode.

[figure not shown]

Figure 8e: Stimulation setup of electrodes for measurement #5.

The resulting table of amplitudes and pulse widths resulting from each measurement will be recorded in the CRF.

This closes part 1 of the efficacy and explant visit. The skin at the location of the Injectrode will now be cleaned once more and prepared for surgical removal of the Basmati Injectrode insert.

Part II: Explant (Device Removal)

Methods:

The explant surgical plan will be verified with images from ultrasound and fluoroscopy taken earlier the same day. The explant is a Mohs style surgery. The injection site is anesthetized via lidocaine (solution 1%), and a sharp cut is made above the Basmati Injectrode. Next, tissue forceps are used to hold onto the device while dissection is performed around the Injectrode in naïve tissue at a target distance of about 0.5 to 1 mm.

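### Measurements 1-4 take the first current felt anywhere as the threshold without asking where it was felt, so a sensation under the return patch would be stored as one at the needle or Injectrode

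*Protocol*

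**What the plan says.** Protocol section 5.0 lists, among the data to be collected, the quality of electrical interfacing with the Injectrode from outside the body, "as well as with subcutaneous sensory nerves surrounding the Injectrode insert". Section 1.4 gives these readings an efficacy role: "The efficacy of the device is assessed by measuring electrical and sensory nerve recruitment data immediately prior to explanting the device".

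Section 9.1.8, Part I, describes how they are obtained. The return electrode is common to Measurements 1-4: "at a location approximately 10 cm away from the Injectrode, a TENS patch electrode will be placed to function as the return electrode". Measurement 1 runs from needle D, 1-2 cm from the Injectrode, to patch C, and the participant reports the first tingling. Measurements 2, 3 and 4 run from needle A, needle B, or both together, to patch C. Each starts no higher than the Measurement 1 threshold. "The study participant will be asked whether they sensed the stimulus, and their answer recorded", and current or pulse duration then rises "until the study participant perceives the stimulus". Measurement 5 runs between needles A and B, and no patch is named. Its threshold is expected to be at least five times that of Measurement 1, which the protocol attributes to shunting through the Injectrode.

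On what is kept, the section says: "The resulting table of amplitudes and pulse widths resulting from each measurement will be recorded in the CRF".

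**The concern.** The current that enters at the needle or Injectrode leaves through the patch, and the skin under the patch also has sensory nerves. The protocol's own background (sections 1.2 and 1.3) says that surface TENS reaches nerves close to the skin, so a sensation under the patch is possible on its own premises. The stopping rule accepts a sensation at either end, and neither the question put to the participant nor the listed CRF content tells the two apart.

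What is at stake is the meaning of the secondary threshold outcome. A value labelled as the threshold of nerves around the Injectrode may be the threshold of nerves 10 cm away. The device is removed in Part II of the same visit, so a doubtful reading cannot be repeated. Section 1.4 intends these data to support a follow-up therapeutic study.

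**Working it through.** The protocol states no figure to reproduce here. The check is one of logic, with a rough scale attached.

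**1. What each measurement records.** At a fixed pulse width, let T_D, T_I and T_C be the currents at which the participant would first feel something at needle D, at the Injectrode (or the needle entering it), and under patch C.
- Measurement 1 records min(T_D, T_C).
- Measurements 2-4 each record min(T_I, T_C), with T_I specific to the contact used.
- Measurement 5 has no T_C term, because no patch is named in its circuit.

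**2. Which Measurement 2-4 readings are safe.** Measurement 1 = min(T_D, T_C), so T_C is at least the Measurement 1 value. Apart from measurement noise:
- A Measurement 2-4 reading below Measurement 1, at the same pulse width, is below T_C and cannot come from the patch.
- A reading at or above Measurement 1 may be T_I or T_C.
- A reading at another pulse width has no matching bound on T_C. Section 9.1.8 allows 50 to 1500 µs. At 10 mA, charge per pulse is 10 mA × 200 µs = 2 µC, against 10 mA × 1500 µs = 15 µC, and the patch receives the same increase.

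The tests start at or below the Measurement 1 value and are described only as rising. A test that starts exactly at that value and is felt at once therefore gives a reading equal to Measurement 1, which is in the ambiguous group.

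**3. Illustration (assumed thresholds).**
- T_I = 3.0 mA and T_C = 2.0 mA: 2.0 mA is recorded as the Injectrode threshold.
- T_I = 3.0 mA and T_C above 3.0 mA: 3.0 mA is recorded, correctly.

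**4. Effect on the fivefold expectation (assumed thresholds).** Take T_D = 3.0 mA, T_C = 2.0 mA and a Measurement 5 threshold of 10 mA.
- Recorded ratio: 10 / min(3.0, 2.0) = 10 / 2.0 = 5.0.
- Ratio to the threshold at needle D: 10 / 3.0 = 3.3.

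The difference comes only from the patch being in one circuit and not in the other.

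**5. How plausible a patch sensation is.** Patch area is not stated; 4 to 25 cm² is assumed. The Injectrode is treated as a solid 10 × 4 × 1.75 mm block (section 3.1) with current spread evenly over it.
- Block surface: 2 × (10×4 + 10×1.75 + 4×1.75) = 129 mm² = 1.29 cm². With the synopsis height of 2 mm: 2 × (40 + 20 + 8) = 136 mm² = 1.36 cm².
- Mean density at the Injectrode relative to the patch = patch area / 1.29.
- Injectrode current giving the density that the patch has at 10 mA = 10 × 1.29 / patch area.

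| Assumed patch area | Density ratio | Equivalent Injectrode current |
|---|---|---|
| 4 cm² | 3.1 | 3.2 mA |
| 10 cm² | 7.8 | 1.3 mA |
| 25 cm² | 19.4 | 0.5 mA |

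On these assumptions the Injectrode would usually be felt first, and low thresholds are unlikely to be affected. Readings of several mA are the ones in doubt.

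**The case against.** The strongest reply is that the design already contains a partial control. Measurement 1 uses the same patch in the same session, and the stored amplitudes and pulse widths identify the readings that lie below it. This stands. A reader might infer that none of the Measurement 2-4 thresholds can be attributed, or that nothing can be recovered afterwards. Neither follows; the doubt is confined to readings at or above Measurement 1 or at a changed pulse width.

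A reader might also infer that the error always favours the device. For a single Measurement 2-4 value the shift can only be downward. But Measurement 1, the natural reference, can be shifted downward in the same way, so a comparison with it can err in either direction. The protocol sets no success limit for Measurements 2-4, and a reading well above Measurement 1 would look unfavourable, so a finite threshold is not in itself a pass.

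Three further points are fair.
- The scale calculation rests on an assumed patch area and on uniform current over a solid block, whereas the device is a mesh of fine wire contacted by needles.
- The CRF template (SOP-36-F3) is listed in section 18.1 but not shown, and it might hold a location field. Section 9.1.8 names only amplitudes and pulse widths and does not instruct staff to ask for a site.
- Impedance, the other half of the secondary outcome, comes from the oscilloscope and does not depend on where anything is felt.

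These points limit the size of the problem. They do not supply the missing question.

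**Conclusion.** The point holds in a limited, conditional form. If a sensation arises under the patch in Measurements 1-4, the procedure as written would record it as the threshold at the needle or Injectrode. Measurement 2-4 readings below the same participant's Measurement 1 value at the same pulse width are free of this ambiguity; the others cannot be attributed to nerves around the Injectrode. A Measurement 5 to Measurement 1 ratio of five or more could partly reflect removal of the patch from the circuit and is not clean evidence of shunting.

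The documents do not show how often this would occur, and it would be wrong to read them as showing that it does. On the assumed patch areas it is probably uncommon at low currents. With at most 10 participants receiving the device, one affected participant is at least 10% of the data, but that describes the sample size and not the frequency. The measure is secondary and descriptive in an unpowered pilot, and the histological primary outcome is untouched. This is a cheap improvement to a measurement rule, worth making before the first explant visit. The conclusion assumes that the three Injectrode-to-patch tests are Measurements 2-4, as their individual descriptions indicate, although the sentence introducing them cites Figures 8c-8e.

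**What to change.** In section 9.1.8, Part I:
- After each reported perception in Measurements 1-5, ask where it was felt (over the Injectrode or needle, under the patch, elsewhere) and record the answer beside amplitude and pulse width in the CRF table.
- For Measurements 2-4, define the Injectrode threshold as the lowest current felt over the Injectrode.
- Where no such sensation is reported within the protocol's existing stimulation limits, record *not felt at the Injectrode up to the highest current tested* in place of a threshold, and report the number of such participants.
- Report the Measurement 5 to Measurement 1 ratio together with the recorded site for Measurement 1.

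The question will not separate the needle shaft from the Injectrode beneath it, but it does separate both from the patch.

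Cost: one question per reported perception and one CRF column, with no added procedure, visit or participant. If the CRF template already has a site field, only the wording in section 9.1.8 needs to change.

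### Section 9.1.8 images needle position but does not check electrical contact with the Injectrode before Measurements 2-4; the only direct A-to-B circuit comes last

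*Protocol*

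**What the plan says.** All of this is in protocol section 9.1.8, Part I, unless another section is named.

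- **Position.** The test setup is imaged in two ways: "First, visualization is done via ultrasound according to a Mohs' surgery plan", and then "Second, the setup is visualized with fluoroscopy to ensure that the needles are placed precisely within the subcutaneously implanted Basmati Injectrode".
- **Insertion.** "Two 30 gauge needles are inserted through the cleaned skin into the Injectrode as shown in Figures 8a through 8e". A third needle, D, goes in 1-2 cm away, and a patch, C, about 10 cm away. The leads are taped down to keep them "from pulling on the needles should the study participant or lead move".
- **Condition for starting.** "Once the leads are properly attached to the needles and TENS patch, testing may commence". This concerns the leads and sets no electrical value for contact between needle and metal.
- **Sequence.** Measurement 1 runs from D to C, 2 from A to C, 3 from B to C, and 4 from A and B joined to C. For Measurement 5: "Lastly, needles A and B will be hooked up to the stimulator as shown in Figure 8e".
- **Use.** Under Measurement 5: "Recorded data from the oscilloscope will be used to calculate the impedance of the Basmati Injectrode". The threshold there is expected to be at least five times that of Measurement 1, because the Injectrode should short-circuit the two needles. Current is raised to 10 mA at most.

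Section 2.2 makes impedance and stimulation threshold the secondary outcome. Section 8.3 limits the study to 10 implanted participants, and section 11.2 states that it is not powered.

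**The concern.** Measurements 2 to 5 can be read as results for the Injectrode only if the needles in use touch its metal. The device is a mesh of 25 micron wire (section 3.1), and the rodent histology in section 1.7 describes a fibrous capsule and collagen fibres around such wires. A needle can therefore lie inside the outline on an image and still sit in tissue.

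In that case Measurement 2 or 3 is close to a repeat of Measurement 1, a needle in tissue against the patch, but carries the Injectrode label. Measurement 5 would lack the expected short circuit, and its trace would still be converted to an Injectrode impedance. Poor contact and poor conduction by the device would be hard to separate.

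The reading that bears most directly on contact comes when Measurements 2-4 are already complete. Section 9.1.8 does not say to repeat any of them if it looks wrong. The visit then moves to explant, after which the data cannot be collected again. Sections 1.4 and 2.2 rely on these data to describe interfacing and to support the follow-up study.

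**Working it through.** The protocol states no figure for contact, so there is nothing to reproduce. The check sets the steps side by side and adds two small calculations.

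**1. What each step shows about contact**

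| Step | Circuit | Bearing on contact of A and B |
|---|---|---|
| Imaging | none | position only |
| Measurement 1 | D to C | none; neither A nor B is in the circuit |
| Measurements 2, 3, 4 | A, B, A+B to C | indirect; each includes the tissue path to a patch about 10 cm away |
| Measurement 5 | A to B | direct, but last |

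No step before Measurement 2 tests contact electrically. No stated rule links Measurement 5 back to Measurements 2-4.

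**2. How far the Measurement 5 threshold can serve as a check afterwards**

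Inputs: cap 10 mA and expected ratio at least 5, both from section 9.1.8. A fivefold rise can be observed only if the Measurement 1 threshold is at most 10 / 5 = 2.0 mA. Above that, the cap is reached before the expected rise. The A-to-B impedance does not depend on this limit, so it is the better check.

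**3. How often it might matter (assumption)**

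The protocol gives no rate. Let *p* be the chance that one needle lacks contact despite acceptable imaging, independent between needles and participants.

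- Per participant, at least one of two needles: *q* = 1 − (1 − *p*)².
- At least one of 10 participants: 1 − (1 − *q*)¹⁰.

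| *p* | *q* | Expected among 10 | At least one of 10 |
|---|---|---|---|
| 1% | 0.0199 | 0.2 | 18% |
| 2% | 0.0396 | 0.4 | 33% |
| 5% | 0.0975 | 1.0 | 64% |
| 10% | 0.19 | 1.9 | 88% |

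The imaging step exists to keep *p* low, so the upper rows should not be taken as likely. Each affected participant is at least 1/10 = 10% of the secondary data.

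**The case against.** Several points against the concern are sound.

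- **Imaging targets this failure.** A reader might infer that a needle outside the mesh passes unnoticed and is recorded as a device result. The documents do not support that: fluoroscopy, with ultrasound, is prescribed to make sure the needles lie within the device. What remains is the narrower case of acceptable imaging without metallic contact.
- **The taping is a safeguard.** It is there to prevent pull on the needles and is not evidence that they move.
- **Taking A to B last does not lose the information.** The needles go in once and no move is planned, so a low final impedance supports contact in Measurements 2-4 and a high one casts doubt on them. Comparing the A-C, B-C and A+B-C traces could help too, although the protocol does not prescribe it. It is therefore too strong to say that needle and device problems can never be told apart.
- **Repetition is not forbidden.** Anaesthetic and explant come only after Part I closes, and a further threshold at another pulse width is allowed. But no step prompts a repeat because of doubtful contact.
- **A needle-to-needle impedance item is in the schedule of events**, listed above the thresholds. Row order does not fix time order, and the detailed text places that circuit last.
- **No rule calls a high reading a device failure.** The fivefold figure is an expectation.
- **Depth.** If the tunnel roof were at 2 mm and the tunnel 5 mm wide (section 9.1.6), a 1.75 mm device could have its upper face as deep as 2 + 5 − 1.75 = 5.25 mm, against needles inserted about 5 mm (section 1.5). A reader might infer that needles will fall short. That reading takes the approximate 2 mm depth as the roof, which the text does not say, and treats about 5 mm as a fixed stop, whereas the needles are guided into the device under imaging.

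**Conclusion.** The point holds as a gap in the order of measurement. Position is checked at setup, but electrical contact is not checked before Measurements 2-4, and the direct A-to-B reading arrives when a problem can be suspected but no reading has been repeated.

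Its reach is limited to the secondary interfacing outcome in up to 10 participants of an unpowered pilot; the primary safety outcome is untouched. How often contact would fail despite acceptable imaging is unknown, and the 18% to 88% range rests wholly on assumed rates of 1% to 10% per needle. The case for acting is that the data can be collected once only and the remedy is very cheap. This is a worthwhile improvement to the procedure, not a flaw that invalidates the study.

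**What to change.** In section 9.1.8:

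1. After Measurement 1 and before Measurement 2, record the A-to-B impedance at a current below that participant's Measurement 1 threshold. It has to follow Measurement 1 because that threshold is not known earlier. Keep Measurement 5 as the closing reading.
2. If the early reading does not indicate a low-impedance path, re-check needle position under the imaging already in use and repeat the reading before going on.
3. Record on the CRF both the first A-to-B reading and any taken after adjustment.
4. Report Measurements 2-5 for all participants, with a flag where contact was not shown.

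Two variants should be avoided. Excluding participants by a bench-derived limit would select on A-to-B impedance, which is itself part of the secondary outcome, and could remove genuine results where tissue has raised it. Taking the first unadjusted reading as the device impedance even when it is known to show no contact would recreate the problem.

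The cost is about a minute of measurement with the same equipment, extra CRF entries and occasional needle re-adjustment. One caveat belongs in the text: a high A-to-B reading may also reflect tissue or encapsulation after 28 days, so a flag is not proof that a needle missed.
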